14.7 Definition of Attribution

The attribution of an AE to the study drug will be determined by the PI or designated physician co/sub-investigator. The PI or designee will record the determination of attribution on the

appropriate AE or SAE form. The attribution of an AE to the investigational drug or to a study procedure will be determined using the descriptors in the following table. For the purpose of this study, in addition to all study medications, the following procedures will be considered when determining attribution:

Code	Descriptor	Definition (guidelines)
UNRELATED CATEGORY		
1	Unrelated	The adverse event is clearly not related to study. The event is completely related to an etiology other than the study product or study intervention (the alternative etiology must be documented in the study subject's medical record)
2	Unlikely	The adverse event is doubtfully related to study and likely to be related to factors other than study product or study intervention.
RELATED CATEGORIES		
3	Possible	The adverse event may be related to study. There is an association between the event and the administration of study product and there is a plausible mechanism for the event to be related to the study product; there may be also an alternative etiology, such as characteristics of the subject's clinical status and/or underlying disease
4	Probable	The adverse event is likely related to study. There is (1) an association between the event and the administration of study product or study intervention, (2) a plausible mechanism for the event to be related to the study product, and (3) the event could not be reasonably explained by known characteristics of the subject's clinical status and or an alternative etiology is not apparent
5	Definite	The adverse event is clearly related to study. There is (1) an association between the event and the administration of the study product or study intervention, (2) a plausible mechanism for the event to be related to the related to the study product, and (3) causes other than the study product have been ruled out and/or the event re-appeared on re-exposure to the study product

For additional information and a printable version of the NCI-CTCAE manual, the NCI-CTCAE website: <http://ctep.cancer.gov/reporting/ctc.html> will be consulted. In a clinical trial, the study product/intervention will always be suspect when attributing an AE and the "unrelated" attribution will be used only when there is an undisputable or likely alternative explanation for the AE.

14.8 SAE Reporting Criteria and Procedures

The PI will be notified by the study staff as soon as a study staff member becomes aware of the SAE. In the absence of the PI, a physician sub-investigator will be notified. An unexpected, non-serious AE that is of Grade 3 severity or higher and study related will be recorded and reported

under the SAE reporting procedure.

14.8.1 Notifying the IRB and DSMB

The PI will submit all safety reports on an ongoing basis to the DSMB. Individual or clusters of SAEs may be reported expeditiously to the DSMB upon determination. The PI determines causality (definitely not related, probably not related, possibly related, probably related, definitely related) of the AE. The DSMB Chair may request further information if necessary and possibly request changes to the protocol or consent form as a consequence of the AE. A back-up notification system will be instituted so that any delays in review by the Chair beyond a specified period of time are forwarded to a secondary reviewer.

SAE's that are **life-threatening/disabling or result in death of research participant; AND unexpected; AND related to the research** must be reported to the sponsor within 24 hours of learning of the event. The sponsor/investigator will report the event to the IRB and DSMB promptly. Investigators must report all other SAEs to the DSMB within **5 working days** (of learning of the event).

The PI will ensure the timely dissemination of SAE information, including expedited reports, to the IRB in accordance with IRB regulations and guidelines. Events that will be reported to the IRB but **do not require prompt reporting**

1. Reasonably anticipated ("expected") potential risks and adverse events *described in the Informed Consent Process and listed on the Informed Consent Form.*
2. Deaths not attributed to the research and deemed *not related to the research* (no connection between the study procedures and the death) do not require prompt reporting.
3. Protocol deviations or violations *not involving risks to participants or unlikely to recur*
4. Data Safety Monitoring Board reports, interim analyses, or other reports, findings, or new information *not altering the risk/benefit profile*
5. Investigator Brochure updates not involving safety information
6. Problems or findings not involving risk (unless the information could affect participants' willingness to continue in the research)

Events that require **prompt reporting** to the IRB

1. Unanticipated problems involving risks to participants and others
2. Adverse events that are unexpected, related to the research, and involve new or increased risk to participant or others
3. Significant protocol deviations (or other accidental or unintentional changes to the protocol or procedures) involving safety or integrity risks or with the potential to reoccur
4. Complaints made by research participants indicating an unanticipated event, or complaints that cannot be resolved by the research staff
5. Unapproved changes made to the research to eliminate an apparent immediate hazard to a research participant

6. Data and Safety Monitoring Board (DSMB) reports, interim analyses, or other oversight committee/monitoring reports/recommendations altering the risks/benefit profile
7. New information indicating an unexpected change in risks or potential benefits
8. Investigator's Brochure (IB or IDB) updates or revisions to safety information
9. Other unanticipated problems such as breach of confidentiality, loss of study data or forms, etc. that could influence the safe conduct of the research

14.8.2 Notifying the FDA

The Investigational New Drug (IND) sponsor (PI) is responsible for the Food and Drug Administration (FDA) safety submissions as follows: The IND Sponsor for this study will handle all regulatory communications with the FDA and will be responsible to update the IND to include this trial, file all regulatory related issues including any MEDWATCH reports which will be reviewed and approved by the PI and Steering Committee. The IND sponsor will be responsible for submission of yearly reports and final report for this study. All DSMB recommendations will be communicated to the IND sponsor in a timely fashion.

The following process for reporting a serious adverse event ensures compliance with the ICH guidelines, 21CFR §312.32.

- Expedited safety report to the FDA applies if the adverse event is classified as one of the following:
 - Serious and unexpected suspected adverse reaction (SUSAR) (Sections 14.3.4, 14.3.6, and 14.7) (i.e. serious, unexpected, and related)
Or
 - Aggregate analysis of adverse events that suggest a causal relationship to the study medications
Or
 - Any findings from clinical, epidemiological, pooled analysis of data pooled across multiple studies, published or unpublished scientific papers or any findings from animal or in vitro testing that would result in a safety-related change in the protocol, informed consent, investigator brochure or other aspects of the overall conduct of the trial will be reported.

Expedited Safety Reports must be reported by the IND Sponsor to the FDA within 15 calendar days; fatal or immediately life-threatening serious, unexpected, suspected adverse reactions must be reported within 7 calendar days. SAEs that do not strictly fit the above criteria may be reported to the FDA in an expedited manner if the IND Sponsor chose to do so. Each 7-day report must be followed up by a 15-day report.

The following types of SAEs will be reported in the IND Annual Report:

- Serious, expected, suspected adverse reactions
- Serious but not a suspected adverse reaction

For standard reporting, the IND Sponsor or designee will file the IND Annual Report. All AEs (not just those requiring 24 hour reporting) will be reported in the Annual IND Report.

14.9 Reporting Pregnancy

A research subject will be terminated from the study due to pregnancy. The PI will be informed immediately of any pregnancy and will report all pregnancies within 24 hours of becoming aware of the event to DSMB utilizing the SAE report form. This report is for tracking purposes only. All pregnancies that are identified during the study will be followed to conclusion and the outcome of each will be reported. The PI will discuss with the participant and/or the treating physician the known possible risks of the investigational product(s) on the fetus. Monitoring of the participant will continue until the conclusion of the pregnancy, and a follow-up SAE report form detailing the outcome of the pregnancy will be submitted to the DSMB. Due to the short study time (maximum of 14 days), and the exclusion of pregnant women from study participation, we do not anticipate having to report pregnancy as part of this study.

14.10 Non-serious adverse events reporting

14.10.1 Notifying the data and safety monitoring board

The DSMB will be notified of non-serious AEs during their regularly scheduled meetings. The events will be presented to the Board in tabular format.

14.10.2 Notifying the Institutional Review Board

The PI will ensure the timely dissemination of AE information to the IRB in accordance with applicable regulations and guidelines.

14.10.3 Notifying the FDA

The IND sponsor (the Study Chair) will file all adverse events per 21 CFR 312.32, whether expedited or part of the IND Annual Report. The IND sponsor will be responsible for compiling the IND Annual Report.

14.10.4 Unanticipated Problems

The Office for Human Research Protections (OHRP) considers unanticipated problems involving risks to subjects or others to include, in general, any incident, experience, or outcome that meets **all** of the following criteria:

Unexpected in terms of nature, severity, or frequency given (a) the research procedures that are described in the protocol-related documents, such as the IRB-approved research protocol and informed consent document; and (b) the characteristics of the subject population being studied;

Related or possibly related to participation in the research (“possibly related” means there is a reasonable possibility that the incident, experience, or outcome may have been caused by the procedures involved in the research); and

Suggests that the research places subjects or others at a greater risk of harm (including physical, psychological, economic, or social harm) than was previously known or recognized.

Incidents or events that meet the OHRP criteria for unanticipated problems will be reported to the DSMB and IRB, in the following time frames:

1. Unanticipated problems that are SAEs should be reported to the IRB within 1 week of the investigator becoming aware of the event.
2. Any other unanticipated problem should be reported to the IRB according to the IRB's reporting policies.

14.11 Data Management

All study data will be collected via systems created by using Research Electronic Data Capture (REDCap, an online data management software) and will comply with all applicable guidelines regarding patient confidentiality and data integrity. Data access in REDCap is password protected and limited to authorized study personnel. All paper records will be kept in secure files in locked cabinets inside locked offices with access limited to authorized study personnel. All other study specific documents and logs will be stored on computer drives hosted and protected by the University of Cincinnati policies with regular back-ups.

14.11.1 Registration

Registration of participants on this protocol will employ an interactive data system in which the clinical site (University of Cincinnati) will attest to the participant's eligibility as per protocol criteria and obtain appropriate informed consent. IRB approval for the protocol must be obtained before accrual can occur from the clinical site.

Each participant enrolled will be assigned a local identifier by the enrollment site. This number can be a combination of the site identifier (location code) and a serial accession number. Only the registering site will have access to the linkage between this number and the personal identifier of the subject.

14.11.2 Data Entry

Data collection for this study will be accomplished with online electronic case report forms. Using encrypted communication links, on-line forms will be developed that contain the requisite data fields.

14.11.3 Data Quality and Monitoring Measures

As much as possible data quality is assessed at the data entry point using intelligent on-line data entry via visual basic designed screen forms. Data element constraints, whether

independent range and/or format limitations or ‘relative’ referential integrity limitations, can be enforced by all methods employed for data input. Quality assurance reports assess data quality post-data entry. As we note, data quality begins with the design of the data collection forms and procedures and incorporates reasonable checks to minimize transcription and omission errors. Of the more important quality assurance measures are the internal validity checks for reasonableness and consistency.

The DSMB will review data quality on an ongoing basis. A risk-based monitoring plan will be developed to support the study. The purposes of study monitoring are to ensure the safety and welfare of study participants and to confirm the accuracy of study data.

An onsite monitoring visit will occur once during the conduct of the trial, with the option of making a second visit if deemed necessary by the PI, to address enrollment, or protocol deviation issues. The Monitoring Plan will detail the frequency and level of intensity of on-site monitoring visits. In general, the study will be monitored for all participants at a level of 100% of study data gathered for inclusion and exclusion criteria, informed consent procedures, AEs and unanticipated problems. The study monitor(s) will collaborate with the PI to conduct remedial site training to ensure compliance with GCP and all regulations.

During scheduled interim remote monitoring visits, the clinical monitors will verify that the protocol is being followed and that data are being collected according to protocol requirements. The clinical monitor(s) will review the Study Regulatory File to determine that all required documentation is being collected and that the IRB approval for the site is current. The monitor will then verify that each participant has signed the correct version of the ICF, and that this document is filed in the participant’s source documents. At each visit, the monitor will perform an audit of the source documents in the subject’s binder by checking them against the database. AE documentation will be checked for completeness and accuracy. At the study closeout, the monitor(s) will confirm that all data have been reviewed, all source documents have been verified, and all required documents are present in the Study Regulatory File.

Protocol deviations and unanticipated problems will be reviewed by the PI, and the regulatory and monitoring staff to determine the need for corrective and preventative action (CAPA). In the event that corrective and/or preventative action is warranted, a root cause analysis will be performed and a CAPA will be completed as per institutional policy. The PI is responsible for communicating the CAPA plan to appropriate staff (i.e. Site Investigator, study team) and obtaining appropriate signatures to address the issues at hand. The PI will work with regulatory and monitoring staff to ensure that the CAPA is followed and is effective in resolving the issue(s). Protocol deviations and unanticipated problems will be reported to the IRB as per institutional policy.

The table below describes the variables to be reviewed during monitoring visits.

Variable	% of Records Reviewed
Informed consents	100%
Eligibility criteria for all screened subjects	100%

Adverse events	100%
Protocol adherence	20% of active subjects
Verification of REDCap with source documents	20% of active subjects
Central study files-inclusion of all applicable documents	100%
Protocol deviations/violations	100%

14.12 Protocol Deviations

The practices below are consistent with Good Clinical Practice (GCP ICH E6) Sections:

- Compliance with Protocol, sections 4.5.1, 4.5.2, and 4.5.3
- Quality Assurance and Quality Control, section 5.1.1
- Noncompliance sections 5.20.1, and 5.20.2

14.12.1 Protocol deviation Definition

14.12.1.1 Protocol Deviation - Any change, divergence, or departure from the study design or procedures of a research protocol that affects the subject's rights, safety, or well-being and/or the completeness, accuracy and reliability of the study data constitutes a protocol violation. Changes or alterations in the conduct of the trial which do not have a major impact on the subject's rights, safety or well-being, or the completeness, accuracy and reliability of the study data are considered non-major protocol deviations. Site Principal Investigator is responsible for reporting protocol deviations to the IRB using the standard reporting form. As a result of deviations, corrective actions are to be developed by the site and implemented promptly.

14.12.1.2 Major Protocol Deviation (Protocol Violation) - A protocol violation is a deviation from the IRB approved protocol that may affect the subject's rights, safety, or well-being and/or the completeness, accuracy and reliability of the study data.

If the deviation meets any of the following criteria, it is considered a major protocol deviation. However, the lists of deviation examples that follow are not exhaustive.

- The deviation has harmed or posed a significant or substantive risk of harm to the research subject.

Examples:

1. A research subject received the wrong treatment or incorrect dose.
2. A research subject met withdrawal criteria during the study but was not withdrawn
3. A research subject received an excluded concomitant medication.

- The deviation compromises the scientific integrity of the data collected for the study.

Examples:

1. A research subject was enrolled but does not meet the protocol's eligibility criteria.
2. Changing the protocol without prior IRB approval, except for modification to ensure the

safety of study participants.

3. Inadvertent loss of samples or data.
 - The deviation is a willful or knowing breach of human subject protection regulations, policies, or procedures on the part of the investigator(s).

Examples:

1. Working under an expired professional license or certification.
2. Failure to follow federal and/or local regulations.
3. Repeated minor deviations.

- The deviation is inconsistent with the NIH Human Research Protection Program's research, medical, and ethical principles.

Examples:

1. A breach of confidentiality.
2. Inadequate or improper informed consent procedure.

14.12.1.3 Non-Major Protocol Deviation - A non-major protocol deviation is any change, divergence, or departure from the study design or procedures of a research protocol that has not been approved by the IRB and which does not have a major impact on the subject's rights, safety or well-being, or the completeness, accuracy and reliability of the study data.

14.12.2 Reporting Protocol Deviations

Deviations from the protocol are not allowed. It is the responsibility of the study site to use continuous vigilance to identify and report any protocol deviations. Upon determination that a protocol deviation has occurred, the study staff will notify the PI and complete the Protocol Deviation form. The PI will complete and sign the Protocol Deviation form and submit it to the IRB, per IRB regulations. Major protocol deviations will be reported to the DSMB at the regular DSMB reporting interval.

15. Statistical considerations

Sample size determination: In a study evaluating 201 hospitalized patients with COVID-19 in China, 82% (165 patients) required supplemental oxygen. Among the patients needing supplemental oxygen, 40% (67 patients) progressed to require advanced respiratory support during their hospital stay.⁸ Considering the fact that our study inclusion criteria mandates the need for supplemental oxygen and the presence of at least one additional poor prognostic biomarker, we anticipate that 50% of our control group will progress to require advanced respiratory support during their hospitalization. We expect that treatment with sirolimus will reduce the need for advanced respiratory support to 25%.

The goal of this pilot study is to determine a meaningful treatment difference in order to conduct a larger confirmatory trial. Given the limited data on treatment responsiveness in COVID-19 populations, we examined various enrollment sizes commensurate with planning a pilot study. Specifically, we undertook a recommended approach for pilot studies in clinical research, which is to not perform hypothesis testing with a significance level set at the traditional value of 0.05.³⁴⁻³⁷ The confidence intervals for the treatment difference were calculated based on demonstrating a reduction in the proportion of subjects needing advanced respiratory support from 0.50 in the placebo group to 0.25 in the sirolimus group. Various levels have been proposed as optimal thresholds for the tolerance of type I error in the context of pilot studies, with the highest being $p=0.25$.³⁴ We chose the type I error rate of 0.2 to denote significant treatment effect between the treatment and placebo arms in our study, as proposed by Stallard.³⁷ A sample size of 30 patients randomized in a 2:1 fashion in favor of sirolimus will allow us to estimate the treatment differences with 80% confidence based on a binomial two-proportion test. A two-sided test will be used since we are unsure if the treatment will have a beneficial effect in this patient population.

Data Analysis Plan: The primary endpoint of this study is progression to respiratory failure requiring advanced support measures. The difference in proportions of progression between the placebo and sirolimus groups and the 80% confidence interval will be calculated. If the confidence interval for the difference in proportions does not include zero, then we will conclude that the treatment difference is clinically meaningful. Considering the small sample size of our study, the significant impact of age and other pre-existing conditions such as diabetes mellitus on overall prognosis in patients with COVID-19 cannot be accounted for in the primary analysis. Patients will be randomized according to a computer-generated permuted block randomization stratified on age: <50 years, 50 – 64 years, and ≥ 65 years. In case recruitment lags we will add external study sites. In such a scenario, University of Cincinnati and the facilities of the affiliated health systems UC Health, LLC and University of Cincinnati Physicians Company, LLC will follow the same randomization scheme. In case of other external sites, randomization will be stratified based on site in addition to the above-mentioned age-based stratification. As exploratory analysis, we will conduct analyses examining differences based on other prognostic factors and concomitant medications such as corticosteroids, hydroxychloroquine, azithromycin etc. An intent-to-treat analysis will be performed for the primary outcome.

16. Identification and access to source data

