
	
had a more robust CD8 T cell adaptive immune response compared to patients with severe disease.
 
Sirolimus (rapamycin) is a macrolide produced by Streptomyces hygroscopicus that complexes with FKBP-12 and binds to and inhibits the mechanistic target of rapamycin (mTOR) pathway. Sirolimus is primarily used as an immunosuppressive agent to prevent rejection in organ transplant recipients. However, in contrast to its role as an immunosuppressive agent in the renal transplant population, sirolimus has been demonstrated to exert an immunostimulatory effect on CD8 T lymphocytes in response to viral infections. In addition, sirolimus has been shown to have an inhibitory effect on the replication of a variety of different viral pathogens, including a related coronavirus, MERS-CoV. In a single center trial, the addition of sirolimus to standard of care treatment resulted in faster viral clearance and improved oxygenation in critically ill patients with H1N1 influenza. Inhibiting the mTOR pathway has been shown to reduce mortality in a murine influenza model, upregulate antiviral gene expression, and boost the response to influenza vaccination in elderly patients. Lastly, a recently conducted pharmacology network analysis has suggested mTOR inhibition as a potentially useful strategy in patients infected with SARS-CoV-2.

Clinical Phase	II
Principal Investigator	[name], University of Cincinnati, Cincinnati OH
Participating Site(s)	University of Cincinnati - Cincinnati, OH
Accrual Objective	30 subjects
Study Objectives	The main objective of our study is to determine if treatment with sirolimus can improve clinical outcomes in hospitalized patients with COVID-19. Based on the results of this trial, additional phase III clinical development trials may be designed.
Study Design	Randomized, double blind, placebo-controlled study design
Dose and Duration of study drug	Sirolimus will be given as a 6mg oral loading dose on day 1 followed by 2mg daily for a maximum treatment duration of 14 days or until hospital discharge, whichever happens sooner.

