10.2 Importance of the knowledge to be gained

The knowledge gained from this study may benefit many subjects with COVID-19, and other similar viral illnesses. The information obtained may improve the scientific community's understanding of the management of COVID-19. Specifically, the study will identify the safety and efficacy of sirolimus in hospitalized patients with COVID-19 and thus may alter the clinical approach to patients with this and other similar viral diseases.

[figure not shown]

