13.3 Participant replacement

Participants with early termination from this study will be replaced if they are deemed non-evaluable.

14. Data and Safety Monitoring Plan

The study protocol will be reviewed and approved by the Data and Safety Monitoring Board (DSMB) and the University of Cincinnati IRB prior to study initiation. Participant enrollment may only begin with IRB approved consent forms. This is an interventional exploratory phase II study.

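### The primary conclusion rule calls any 80% confidence interval that excludes zero clinically meaningful, but that shows only significance at two-sided 0.2, and no minimum important difference is stated

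*Combined protocol and SAP*

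**What the plan says.** The Data Analysis paragraph of the synopsis, the Data Analysis Plan in protocol Section 15 and the SAP's Data Analysis Plan carry the same text. First, "The difference in proportions of progression between the placebo and sirolimus groups and the 80% confidence interval will be calculated". Then comes the rule: "If the confidence interval for the difference in proportions does not include zero, then we will conclude that the treatment difference is clinically meaningful".

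The sample size text in the same three places gives this threshold a different name: "We chose the type I error rate of 0.2 to denote significant treatment effect between the treatment and placebo arms in our study". The test is stated to be two-sided.

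The only effect size in the documents is the planning assumption of 50% progression on placebo and 25% on sirolimus. Section 15 presents it as an expectation: "We expect that treatment with sirolimus will reduce the need for advanced respiratory support to 25" percent. A meaningful difference appears as something still to be learned: "The goal of this pilot study is to determine a meaningful treatment difference in order to conduct a larger confirmatory trial".

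On use of the result, the synopsis says: "Based on the results of this trial, additional phase III clinical development trials may be designed". Section 14 opens by stating: "This is an interventional exploratory phase II study".

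**The concern.** An 80% two-sided interval that excludes zero and a two-sided test at alpha 0.2 are in substance the same criterion. The plan gives that criterion two names. The first, significant, fits. The second, clinically meaningful, is a statement about the size of the effect, and the criterion does not examine size beyond asking whether it differs from zero. The 25-point reduction helps to set the sample size but does not appear in the rule.

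The rule also has no direction. As written, an interval lying wholly on the side of harm is called clinically meaningful too.

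This is the only conclusion rule given for the primary endpoint, and later trials may be designed from the result. A prespecified conclusion of clinical meaningfulness from 30 patients can be quoted as an efficacy finding, and the observed difference behind it can be carried into a confirmatory sample size.

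**Working it through.** **Inputs** (Section 15): 30 patients, 2:1, so 10 placebo and 20 sirolimus; planning rates 0.50 and 0.25; two-sided 80% interval, z = 1.2816. Differences are placebo minus sirolimus, in percentage points. The plan does not name the interval method, so results are given for Wald / Newcombe / Miettinen-Nurminen, in that order.

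**1. The plan's own figures.** 1 − 0.80 = 0.20, the stated alpha. The plan does not show how 30 was reached. It is, however, the smallest 2:1 trial in which an observed 50% vs 25% just excludes zero by Wald:

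n(placebo) > z² × (0.25 + 0.1875/2) / 0.25² = 1.6424 × 0.34375 / 0.0625 = 9.03, so 10 placebo and 30 in total.

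The Wald lower limit at exactly those rates is −0.05 points with 27 patients and +1.24 with 30.

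**2. The planned result, 5/10 vs 5/20.** SE = √(0.25/10 + 0.1875/20) = √0.034375 = 0.1854; half-width = 1.2816 × 0.1854 = 0.2376; interval = 0.25 ± 0.2376.

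- Wald: 1.2 to 48.8 points
- Newcombe: 1.6 to 46.4 points
- Miettinen-Nurminen: 1.2 to 47.6 points

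All three earn the label while allowing true effects close to zero. One more sirolimus event (5/10 vs 6/20) gives −4.1 to 44.1 by Wald, and the label is lost.

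**3. How the rule behaves.** All 11 × 21 = 231 possible outcomes were enumerated with exact binomial weights.

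| True rates (placebo vs sirolimus) | Labelled, benefit (%) | Mean observed reduction in those trials (points) |
|---|---|---|
| 50% vs 25% | 55.6 / 56.3 / 53.7 | – |
| 50% vs 40% | 26.0 / 26.1 / 20.8 | 34.1 / 34.1 / 36.4 |
| 50% vs 45% | 18.5 / 18.5 / 13.9 | 33.0 / 33.0 / 35.6 |

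With 50% in both arms the label is given in 24.8 / 24.7 / 18.0% of trials, split equally between benefit and harm.

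**4. What a label establishes when the planning rates are true.** Among benefit labels the median lower limit is about 12 points. It is below 10 points in 37.6 / 38.5 / 37.9% and reaches 25 points in only 20–21%. The documents give no threshold, so the 5-, 10- and 25-point values here and in step 3 are illustrative assumptions.

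**The case against.** The strongest reply is that the anticipated effect does enter the rule, through the sample size. Thirty is the first size at which a 25-point difference excludes zero. With Wald and 3 to 8 placebo events out of 10, the smallest qualifying reduction is exactly 25 points. At the planning rates, 99.97 / 98.6 / 98.5% of benefit labels have an observed reduction of at least 25 points, so the label goes to results about as large as the sponsor hoped for. This is true and limits the finding: near the planned rates, a trivially small observed difference will not be labelled. It does not rescue the label. Only large observed differences can qualify in a trial this small, so a smaller true effect qualifies when chance inflates it; a true 10 points appears as 34–36.

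A second reply is that this inflation comes from small numbers and selection, and would be the same under any wording. That is also right. Rewording will not remove the inflation; it stops the plan from certifying an inflated figure as clinically meaningful.

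Third, little hangs on the label. Alpha 0.2 is openly declared, the trial is described as a pilot and exploratory, no automatic go/no-go decision follows, and the difference and interval are reported anyway. These points make the consequences modest. Against them, Section 10.2 tells readers that "the study will identify the safety and efficacy of sirolimus in hospitalized patients with COVID-19 and thus may alter the clinical approach". That is general benefits text and does not cite the rule, so it carries limited weight, but it shows that the result may be read as more than a pilot signal.

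Finally, demanding a lower limit well above zero would be unrealistic with 30 patients. With placebo at 5/10 and Wald limits, an assumed 25-point margin would be met only by 0/20 on sirolimus. The finding makes no such demand.

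**Conclusion.** The concern holds and should be fixed. The criterion tests only whether the difference is zero at two-sided 0.2, the plan elsewhere calls that same threshold significant, and no minimum important difference is stated. The expected result would be declared clinically meaningful with a lower limit below 2 points by any of the three methods.

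The textual contradiction needs no assumption. The probabilities assume exactly 10 and 20 analysed patients, independent outcomes and the true rates shown. The fault lies in the label and its lack of direction; the 80% level, the sample size and the choice to report an interval are not challenged.

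**What to change.** In the synopsis, Section 15 and the SAP, replace the conclusion sentence with:

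> The difference (placebo minus sirolimus) and its two-sided 80% confidence interval will be reported. An interval wholly above zero will be described as preliminary evidence of benefit at the two-sided 0.2 level; wholly below zero, as a signal of harm; an interval including zero, as inconclusive, stating whether the planned 25-point reduction lies inside it.

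Keep the term clinically meaningful only if a minimum important difference is stated in advance and justified separately. The expected 25 points should not become that minimum by default.

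As a secondary step, name the interval method. At the planning rates Newcombe and Miettinen-Nurminen are both acceptable; their label differs from Wald's in 1.0% and 3.6% of trials. The methods part when events are sparse. Miettinen-Nurminen would call 1/10 vs 0/20 a benefit (lower limit +1.7 points), and Wald would call 0/10 vs 2/20 a harm (upper limit −1.4 points). Newcombe does neither.

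The cost is one sentence in three places and a slightly less favourable stated conclusion. Sample size, data and confidence level do not change. Naming Newcombe or Miettinen-Nurminen moves the chance of a benefit call at 50% vs 25% from 55.6% (Wald) to 56.3% or 53.7%.
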